9.1 STATISTICAL HYPOTHESES

The proposed analysis is primarily descriptive rather than inferential, as it designed to provide a general assessment of participant level behaviors in the context of a community testing intervention. An exploratory hypothesize is that positive at-home SARS-CoV-2 antigen test results will lead to altered self-reported social interactions and altered health behaviors compared to negative test results.

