9.4 STATISTICAL ANALYSES

9.4.1 GENERAL APPROACH

The approach to analysis will be primarily descriptive. Demographics, questionnaire data, and testing results will be reviewed and summarized using graphical techniques and summary statistics. Where applicable, exact method confidence intervals will be computed around point estimates. Trends over time will be evaluated graphically. The proportion of participants adhering to social distancing guidelines after a positive vs. negative test result will be compared using tests of proportion clustered by participants with various levels of intra-participant correlation. Stratified analyses by test or week number will also be performed. We will explore the associations between positive test results and critical behavioral measures using mixed modeling techniques to account for the participant and

household correlations. Analyses will be conducted using SAS (SAS Institute, Cary NC) and R with R Studio (R-project).

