9.4.2 ANALYSIS OF THE PRIMARY EFFICACY ENDPOINT(S)

Point estimates with 95% confidence intervals will be reported. The analysis will be done for applicable study populations as described above, and stratified by participant demographics of interest (e.g., age, gender). There will be a comparison of the proportion of participants that report adhering to social distancing guidelines after positive vs. negative test result.

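### Exact intervals and the participant-clustered comparison leave out household correlation, and the unadjusted comparison cannot carry the causal wording of section 9.1

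*Combined protocol and SAP*

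**What the plan says.** The comparison of adherence after positive and negative results is part of the primary endpoint (sections 1.1 and 3). Section 9.4.2 states: "There will be a comparison of the proportion of participants that report adhering to social distancing guidelines after positive vs. negative test result". Section 9.4.1 gives the method: the proportions will be "compared using tests of proportion clustered by participants with various levels of intra-participant correlation". No covariate is named. The planned strata are test or week number ("Stratified analyses by test or week number will also be performed", section 9.4.1) and demographics (sections 9.4.2 and 9.4.8). Section 6.3 describes the cohort as non-randomised.

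For single proportions, section 9.4.1 says: "Where applicable, exact method confidence intervals will be computed around point estimates". Section 4.1 has test kits going to households. Section 9.4.1 recognises participant and household correlation, but only in a further sentence: "We will explore the associations between positive test results and critical behavioral measures using mixed modeling techniques". Those models list no covariates either, and nor does the multivariable modelling mentioned in section 9.2.

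On purpose, section 9.1 says "The proposed analysis is primarily descriptive rather than inferential" and section 9.4.1 says "The approach to analysis will be primarily descriptive". Yet section 9.1 continues: "An exploratory hypothesize is that positive at-home SARS-CoV-2 antigen test results will lead to altered self-reported social interactions". The synopsis words the same hypothesis as an association. Section 9 defers further detail to a separate statistical analysis plan, which is not among the documents supplied.

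**The concern.** There are two separate issues.

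First, an exact binomial interval assumes independent observations. If several members of one household enrol, or one person contributes several surveys, positively correlated answers make the interval too narrow. The positive-versus-negative test handles repeated results within a person but not similarity between people in one home.

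Second, the test result is not assigned. People who distanced less beforehand may be more likely to test positive, which would pull adherence after a positive result down. People with symptoms may be more likely both to test positive and to stay home, which would push it up. Social interactions are surveyed from Baseline and symptoms are a questionnaire domain (section 1.3), but no section names either as an adjustment variable. A reader who takes section 9.1's verb literally would read an unadjusted contrast as a response to the result.

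**Working it through.** **1. The plan's precision table (section 9.2).** The margin is 1.96 × √(p(1−p)/n). For p = 50% and n = 5,000 this is 1.386%. Multiplying by a finite population correction for the maximum cohort of 300,000, √(295,000/299,999) = 0.9916, gives 1.37%, the printed value. All 12 rows reproduce this way. The correction is inferred, since the plan does not state it. There is no design effect, so the table treats participants as independent.

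**2. Households and single proportions.** The documents give neither the number of enrolled members per household (m) nor the household correlation (ICC). Assume m = 2 to 4 and ICC = 0.1 to 0.3. The design effect is 1 + (m−1) × ICC.
- m = 2, ICC 0.1: 1.10, so the interval should be √1.10 = 1.05 times as wide.
- m = 4, ICC 0.3: 1.90, so √1.90 = 1.38 times as wide.
- At n = 5,000 and p = 50%, 1.386% becomes 1.45% to 1.91%.

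Simulated coverage of nominal 95% exact intervals (beta-binomial households, p = 50%), for m = 2 / 3 / 4:

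| | n = 1,000 | n = 5,000 |
|---|---|---|
| ICC 0.1 | 94.1 / 92.7 / 92.2% | 94.2 / 92.5 / 91.7% |
| ICC 0.3 | 92.2 / 87.8 / 85.1% | 91.7 / 87.4 / 84.7% |

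With one member per household, coverage is about 95%.

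**3. Households and the comparison.** Here household correlation matters only if positive results also cluster. The standard-error ratio is √(1 + (m−1) × rx × 0.3), with rx = (concordance − 0.03)/0.97 at an assumed 3% positive. It is 1.00 with no clustering of positives, 1.05 at m = 2 with 35% concordance, and 1.31 at m = 4 with 80% concordance.

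**4. Prior distancing alone, true effect zero.** Assume 50% adherent at Baseline, non-adherers 1.5 to 3 times as likely to test positive, 80–90% persistence of behaviour, and 1–5% positive. The shift is [P(adherent at Baseline | positive) − P(adherent at Baseline | negative)] × (2 × persistence − 1). At 3% positive:
- ratio 1.5, persistence 80%: (0.400 − 0.503) × 0.6 = −6.2 points
- ratio 3, persistence 90%: (0.250 − 0.508) × 0.8 = −20.6 points

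Across 1–5% positive the range is −6.1 to −21.1 points.

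**5. Symptoms alone, true effect zero.** Assume symptoms in 40–60% of positives and 5–10% of negatives, raising adherence by 20–30 points. The shift is (0.40 − 0.10) × 20 = +6.0 to (0.60 − 0.05) × 30 = +16.5 points.

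**6. Both together.** These inputs were crossed in 243 settings, with symptoms acting on people who would not otherwise adhere. The crude shift runs from −11.8 to +12.6 points, is negative in 40% of settings, and has a median absolute size of 3.8. For scale, the sampling half-width is 196 × √(0.25/(Np) + 0.25/(N(1−p))) points, where p is the proportion positive. At 3% positive it is 8.1 points for N = 5,000 and 5.7 for N = 10,000.

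**7. What adjustment does on the same grid.** The models with symptoms include the Baseline-by-symptom interaction.

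| Adjustment | Remaining shift (points) | Closer to zero than crude |
|---|---|---|
| Baseline adherence only | +6.7 to +23.0 | 2% of settings |
| Both, all pre-test symptoms captured | 0.0 | all |
| Both, 75% captured | +1.8 to +7.3 | 53% |
| Both, 50% captured | +3.6 to +13.4 | 17% |

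A random participant intercept with no covariates, 3 surveys each and prior distancing alone, cuts shifts of about −6, −11 and −20 to about −2.5, −3.7 and −4.4. It does not remove symptom confounding.

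**The case against.** The strongest reply is that the plan calls itself descriptive and labels the hypothesis exploratory. A descriptive contrast needs no confounder adjustment. This stands, and the crude difference should remain the main result. What it does not cover is a causal verb resting on that contrast.

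A reader might infer that the final analysis will be unadjusted. The documents do not show that. Section 9 defers to a separate plan and section 9.2 mentions multivariable modelling, so all that can be said is that no covariate is specified in the supplied text. Nor does the plan ignore household correlation throughout, because the mixed models include it. They may also remove part of the prior-distancing bias, as step 7 shows.

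A reader might also infer that an adjusted model should become the primary analysis. Step 7 argues against it: with incomplete symptom capture the adjusted figure is often no closer to the truth, because the two crude biases partly cancel. Capture may well be incomplete. Questionnaires fall at Baseline and weeks 1, 3, 5, 13 and 21 and may be completed in the week after a test (section 1.3), and the documents do not say that symptom onset is dated.

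Finally, the household effect may be small. If most households enrol one person, the design effect is near 1. That is a fair caveat on size, but in that case the robust interval costs almost nothing.

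**Conclusion.** Both parts hold in a limited form. Where household members or repeated surveys contribute together, exact intervals are too narrow. The loss of coverage ranges from slight to about ten percentage points under the assumed household sizes and correlations, none of which the documents give. The comparison's own standard error is affected only if positives cluster within homes.

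The unadjusted comparison is a legitimate description that cannot support the causal wording of section 9.1, which also conflicts with the synopsis. The supplied documents do not establish the direction or size of any bias: every confounding input above is an assumption, and the two mechanisms oppose each other. The large single-mechanism figures should not be read as expected errors, since the median joint shift of 3.8 points lies inside the sampling half-widths in step 6. Confidence is moderate, because the separate analysis plan may already settle some of this.

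**What to change.** - **Single proportions:** use household-cluster-robust 95% intervals whenever more than one household member or more than one survey per person contributes, and exact intervals otherwise.
- **Comparison:** cluster the positive-versus-negative comparison on household, which also covers repeated results within a person. Keep the crude difference as the main descriptive result.
- **Supporting analysis:** beside it, prespecify the mixed model already planned in section 9.4.1, adjusted for Baseline adherence and pre-test symptoms together, preferably with their interaction. Do not adjust for Baseline alone. Report an adjusted difference in proportions with its 95% interval. State that residual confounding remains and that symptom timing may be coarse. Do not make this model primary.
- **Wording:** in section 9.1, replace *will lead to* with the synopsis's *will be associated with*.

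The cost is analysis-plan text, one changed verb and slightly more analysis. The surveys are already scheduled, and the planned mixed models already need a household identifier. Single-proportion intervals become about 5–38% wider under the assumed household sizes and correlations, and the comparison's interval 5–31% wider if positives cluster as in step 3. A rule is also needed for participants with no Baseline survey before the linked test.

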9.2 SAMPLE SIZE DETERMINATION

A formal power calculation is not performed for this observational cohort study. However, a sample size in the ranges of 1000 to 10,000 participants would be sufficient to estimate positive test incidence and prevalence, describe behavioral changes associated with test results, and conduct multivariable modeling to inform understanding of the causal chain between frequent testing and community burden of disease. To illustrate this, suppose the proportion of participants who adhere to social distancing is 50%. In that case, a sample size of 5,000 participants will be sufficient at a confidence level of 95% to estimate the prevalence with a margin of error of 1.5%. Additional examples of estimate precision at varying sample sizes are provided below. Overall, even with a sample size of 1000 participants and for an endpoint with a 50% proportion, there will be a 95% chance that the real value of this proportion is within 3.1% of the observed value.

Sample Size N=	Point estimate of proportion	Margin of error
10,000	1%	0.19%
10,000	10%	0.58%
10,000	50%	0.96%
10,000	80%	0.77%
5000	1%	0.27%
5000	10%	0.82%
5000	50%	1.37%
5000	80%	1.10%
1000	1%	0.62%
1000	10%	1.86%
1000	50%	3.09%
1000	80%	2.48%

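### The pooled positive-vs-negative comparison of the primary endpoint is specified at several within-participant correlation levels with none designated as the result, although the correlation can be estimated from the data

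*Combined protocol and SAP*

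**What the plan says.** Section 9.4.1 (General Approach) gives the only stated method for the pooled comparison: the proportions after positive and negative results will be "compared using tests of proportion clustered by participants with various levels of intra-participant correlation". It does not list the levels, say whether they are set or estimated, or name the level that supplies the reported result.

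Section 9.4.2 (primary endpoint) promises intervals, "Point estimates with 95% confidence intervals will be reported", and repeats the comparison, "There will be a comparison of the proportion of participants that report adhering to social distancing guidelines after positive vs. negative test result". It gives no variance method.

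Three other statements in Section 9 bear on the point:

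- Section 9.4.1 also plans analyses stratified by test or week number, and then mixed models: "We will explore the associations between positive test results and critical behavioral measures using mixed modeling techniques". These account for participant and household correlation but are not assigned to the primary comparison.
- Section 9.1 states that "The proposed analysis is primarily descriptive rather than inferential" and calls the positive-vs-negative hypothesis exploratory. Section 9.2 adds that "A formal power calculation is not performed for this observational cohort study".
- The opening of Section 9 defers further detail to a separate statistical analysis plan, which is not among the documents supplied.

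The Schedule of Activities (1.3) places the social-interaction questionnaire at baseline and Weeks 1, 3, 5, 13 and 21. Section 4.4 describes testing three times a week for four weeks, which is 12 tests.

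**The concern.** Trying several correlation values is what one does at the planning stage, before there are data to estimate the correlation. Here each participant can supply up to five post-baseline records, and Section 9.2 says that "a sample size in the ranges of 1000 to 10,000 participants would be sufficient", so the analysis will have ample data to estimate it.

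If the comparison is run at several set values and none is primary, the plan yields several standard errors, intervals and p-values for one difference. An interval built on too low a correlation can be too narrow, one built on too high a correlation too wide, and the level to report could be picked after the results are seen. The comparison is part of the primary endpoint in the Synopsis and in Section 3, so its interval should be determined in advance.

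**Working it through.** **The plan's own precision figures.** The table in Section 9.2 is reproduced by 1.96 × √(p(1−p)/N) × √((300,000−N)/299,999). The finite population of 300,000 is my inference from the recruitment ceiling. For p = 50% and N = 1,000: 1.96 × √(0.25/1,000) = 3.10%, times √(299,000/299,999) = 0.998, gives 3.09%, as printed. All 12 entries agree to two decimals. The table counts each participant once and concerns a single proportion, so it says nothing about the clustered comparison.

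**Inputs for the comparison.** The documents give no correlation, positive rate, effect size or definition of a record, so these are assumptions: 5% of participants ever positive, a 10-point difference, and an exchangeable correlation ρ from 0 to 0.8. Let each participant have m records, of which k are positive in an ever-positive participant; n₁ and n₀ are the numbers of positive and negative records.

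**Formula.** Var(difference) = V₁ + V₀ − 2C, where

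- V₁ = p₁(1−p₁)/n₁ × (1+(k−1)ρ);
- V₀ = p₀(1−p₀)/n₀² × Σ s(1+(s−1)ρ), summed over participants with s negative records;
- C is the covariance from participants who contribute to both groups.

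**Several positive records, 3 of 12.** N = 1,000, 60% vs 50%. There are 50 ever-positive participants, so n₁ = 150 and n₀ = 50×9 + 950×12 = 11,850.

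- ρ = 0: V₁ = 0.24/150 = 0.001600; V₀ = 0.25/11,850 = 0.000021; SE = √0.001621 = 4.03 points; p = 0.013.
- ρ = 0.8: V₁ = 0.001600 × 2.6 = 0.004160; V₀ = 0.000205; 2C = 0.000298; SE = √0.004067 = 6.38 points; p = 0.117.

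This assumes one adherence record per test. The survey schedule provides fewer.

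**Several positive records, 2 of 5.** This matches the number of post-baseline surveys. With the same N and proportions, the results are:

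| ρ | SE (points) | p |
|---|---|---|
| 0 | 4.95 | 0.043 |
| 0.1 | 5.18 | 0.053 |
| 0.3 | 5.60 | 0.074 |
| 0.5 | 6.00 | 0.096 |
| 0.8 | 6.55 | 0.127 |

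**Result constant over five surveys.** N = 2,000, 70% vs 60%, true ρ = 0.6; n₁ = 500, n₀ = 9,500, C = 0.

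- Unclustered variance: 0.21/500 + 0.24/9,500 = 0.000445.
- True SE: √(0.000445 × 3.4) = 3.89 points.
- SE if ρ = 0.1 is used: √(0.000445 × 1.4) = 2.50 points.
- The nominal 95% interval then spans ±1.96 × 2.50/3.89 = ±1.26 true standard errors, which is about 79% coverage.

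In simulations of this kind, participant-clustered sandwich standard errors gave coverage of about 94% to 95%.

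**One positive record per positive participant.** N = 1,000, 1 of 5, 60% vs 50%. The SE goes from 6.96 points at ρ = 0 to 6.85 at ρ = 0.8, and p from 0.151 to 0.144. The positive group has clusters of size one and dominates the variance, so ρ hardly enters.

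The exception is a common multiplier 1+(m−1)ρ on both groups. For 2,000 participants, three records each, 70% vs 60%, n₁ = 100 and n₀ = 5,900, the unclustered SE is √(0.21/100 + 0.24/5,900) = 4.63 points. At ρ = 0.8 a common multiplier gives 4.63 × √2.6 = 7.46 points (p = 0.18, against 0.03 at ρ = 0). Inflating each group by its own cluster size gives 4.70, and also subtracting the covariance gives 4.56.

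**The case against.** The strongest reply is that the text never says that the correlations are assumed or that they replace the observed one. A reader might infer this, but the documents do not support stating it as fact: the phrase could describe a sensitivity range, or correlation that differs between participants. That stands as a limit on the claim. It does not remove the gap, because on any of these readings no governing result is named.

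A reader might also infer that even a single positive record makes the result swing widely. That needs a common design effect on both groups, which the plan nowhere specifies. Without it the change is under 2%.

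The plan has partial safeguards. Within one test or week number a participant contributes essentially one result, so the stratified analyses largely avoid the problem. The mixed models would estimate the correlation. Neither is named as the pooled primary comparison.

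The constant-result scenario is also generous to the concern. Testing lasts four weeks and Weeks 13 and 21 are follow-up, so fewer than five surveys may be directly linked to a test.

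Finally, no alpha, power or decision rule is stated, the aim is descriptive, and the separate analysis plan may settle the matter. This lowers the severity. A descriptive 95% interval still needs a valid standard error.

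**Conclusion.** The point holds as a moderate one. The plan does not fix the variance method for the pooled positive-vs-negative comparison, and its wording suggests a grid of correlations where one estimated from the data is available.

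The size depends on the undefined record unit. Over ρ from 0 to 0.8, the standard error changes by a factor of about 1.3 with 2 of 5 positive records (6.55/4.95) and about 1.6 with 3 of 12 (6.38/4.03). With one positive record it changes hardly at all if variances are computed by group. Too low a level could cut the coverage of a 95% interval to about 79% in the constant-result scenario. All these figures rest on the assumed positive rate, adherence, correlation and records per participant.

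A reader might go further and conclude that the primary result is invalid or that significance will turn on a guess. The documents do not support that, since they state no significance rule and declare the analysis primarily descriptive.

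**What to change.** In Sections 9.4.1 and 9.4.2:

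1. Designate one primary analysis: adherence (yes/no) modelled on the test result linked to each survey, with within-participant correlation estimated from the data. GEE with participant-clustered sandwich standard errors, and a small-sample correction when positives are few, is one suitable choice; a mixed logistic model is another.
2. Report the risk difference with its 95% confidence interval.
3. Define the record, that is, which test result attaches to which survey, and say how household correlation enters.
4. Keep any grid of fixed correlations only as a labelled sensitivity analysis.

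If the separate analysis plan already does this, a cross-reference is enough. The cost is a change of wording and slightly more analysis work. The methods are available in SAS and R, which the plan already names, and no new data are needed.

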1 PROTOCOL SUMMARY

1.1 SYNOPSIS

Title:	Rapid Acceleration for Diagnostics in Underserved Populations: Home Testing (RADx-UP HoT)
Study Description:	This observational, cohort sub-study is embedded within a larger public health intervention that distributes at-home, self-administered, SARS-CoV-2 antigen testing kits to households within pre-selected communities through the CDC. Within this sub-study, we will evaluate the socio-behavioral mechanisms of SARS-CoV-2 community transmission, including social interactions, health behaviors, healthcare utilization, knowledge, disease burden, and feasibility of at-home testing. The study hypothesis is that positive at-home test results will be associated with altered self-reported social interactions and altered health behaviors compared to negative test results. Surveys and questionnaires will be completed by participants through the smartphone app or via call center phone calls according to the schedule of events. Questionnaires will collect data on demographic characteristics, medical history and health status, COVID testing and symptoms, social interactions, knowledge of prevention strategies, infection risk, and attitudes towards vaccines.
Objectives:	
Primary Objective:
 
• To assess self-reported social interactions following SARS CoV-2 at-home test result over the study period 
Secondary Objectives:
 
• To assess change in self-reported behaviors before and following SARS CoV-2 at-home test result over the study period• To assess the impact of at-home testing regimen on self-reported healthcare utilization for SARS CoV-2 treatment• To assess knowledge of SARS CoV-2 prevention approaches over the study period
Endpoints:	
Primary Endpoint:
 
• Proportion of respondents that report adhering to social distancing guidelines after a test result; comparison of proportion adherent after positive vs. negative test result 
Secondary Endpoints:
 
• Proportion of respondents that decide to act on precautionary behaviors after a test result• Point estimate and 95% confidence interval for each healthcare utilization measure and composite measure• Proportion of respondents that are knowledgeable of precautionary measures to prevent infection• Prevalence of positive test results with 95% confidence intervals

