5 STUDY POPULATION

5.1 INCLUSION CRITERIA

In order to be eligible to participate in this study, an individual must meet all of the following criteria:

1. Self-reported primary residence within the pre-identified communities
2. Age > 8 years at enrollment
3. Provision of signed and dated informed consent form

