6.3 MEASURES TO MINIMIZE BIAS: RANDOMIZATION AND BLINDING

This study will be conducted as a non-randomized cohort sub-study design to assess the individual social behavior during a community level at-home testing program. Eligible communities receiving will be selected per criteria in the public health intervention.

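### The primary positive-versus-negative comparison pools non-randomly selected communities without stratifying by community, so community differences in positivity and distancing can create or hide a difference

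*Combined protocol and SAP*

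**What the plan says.** The synopsis (section 1.1) includes in the primary endpoint a "comparison of proportion adherent after positive vs. negative test result". Section 9.4.2 repeats it: "There will be a comparison of the proportion of participants that report adhering to social distancing guidelines after positive vs. negative test result".

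The method is in section 9.4.1, where the two proportions are to be "compared using tests of proportion clustered by participants with various levels of intra-participant correlation". The same section adds "Stratified analyses by test or week number will also be performed". Section 9.4.2 stratifies by demographics such as age and gender, and section 9.4.8 adds race/ethnicity or other demographic characteristics. For the exploratory models, section 9.4.1 says "We will explore the associations between positive test results and critical behavioral measures using mixed modeling techniques to account for the participant and" household correlations.

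The sample comes from more than one community. The synopsis describes distribution of "antigen testing kits to households within pre-selected communities through the CDC". Section 6.3 calls the design non-randomized and says "Eligible communities receiving will be selected per criteria in the public health intervention". Section 5.1 requires "Self-reported primary residence within the pre-identified communities". The number of communities is not given. No section names community as a stratum, covariate, fixed effect or random effect.

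**The concern.** Community can be a common cause of both sides of this comparison. Infection levels vary by place, and so may distancing habits and local guidance. Where they vary together, positive results come disproportionately from communities with a particular level of distancing. A crude pooled comparison then partly compares places instead of responses to a result.

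Clustering by participant corrects the standard error for repeated results from one person; it does not move the estimate. A participant or household random effect in the exploratory models uses some within-person information, but in general it does not remove a between-community difference associated with the test result.

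The comparison is likely to be read causally. Section 9.1 hypothesizes that a positive result brings about changed interactions and behaviors, and section 9.2 speaks of informing a causal chain. A spurious difference would be read as a behavioral response to testing, and a masked one as its absence.

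**Working it through.** **The plan's own figure.** The documents give no power, effect size or precision for the positive-versus-negative comparison. The nearest figure is the section 9.2 table for one overall proportion. For N = 5,000 and 50%, 1.96 × √(0.5 × 0.5 / 5,000) = 1.39%. The table's 1.37% follows after a finite population correction, 1.386% × √(295,000 / 299,999) = 1.374%. The 300,000 in that correction is inferred from the fit and from the recruitment ceiling; section 9.2 does not state it. This margin does not describe a difference between two result groups.

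**Inputs for the bias.** The documents give no community-level positivity or adherence, so every rate below is an assumption. There are two communities of equal size, with positivity p₁, p₂ and adherence a₁, a₂, and the result has no true effect within either community.

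- Pooled adherence after a positive: (p₁a₁ + p₂a₂) / (p₁ + p₂)
- Pooled adherence after a negative: [(1 − p₁)a₁ + (1 − p₂)a₂] / (2 − p₁ − p₂)

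**Larger contrast** (1% and 4%; 40% and 60%):

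- Positive: (0.01 × 0.40 + 0.04 × 0.60) / 0.05 = 0.028 / 0.05 = 56.0%
- Negative: (0.99 × 0.40 + 0.96 × 0.60) / 1.95 = 0.972 / 1.95 = 49.8%
- Spurious difference: 6.2 points

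**Milder contrast** (1% and 2%; 45% and 55%):

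- Positive: (0.01 × 0.45 + 0.02 × 0.55) / 0.03 = 0.0155 / 0.03 = 51.7%
- Negative: (0.99 × 0.45 + 0.98 × 0.55) / 1.97 = 0.9845 / 1.97 = 50.0%
- Spurious difference: 1.7 points

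**When it vanishes.** The crude difference equals (a₂ − a₁) × (community 2's share of positives − its share of negatives). In the larger case this is 0.20 × (0.80 − 0.96/1.95) = 0.20 × 0.308 = 6.2 points. It is zero if a₁ = a₂ or p₁ = p₂. A comparison within community returns zero in both cases above.

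**Masking.** Take a true +5 points in each community, positivity of 1% and 3%, and adherence after a negative of 60% and 40%.

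- Positive: (0.01 × 0.65 + 0.03 × 0.45) / 0.04 = 50.0%
- Negative: (0.99 × 0.60 + 0.97 × 0.40) / 1.96 = 50.1%
- Crude difference: −0.1 points; the stratified comparison returns +5

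**Bias against sampling error.** Assume one result per participant and adherence near 50%. The 95% half-width of the difference is 1.96 × √(0.25/n₊ + 0.25/n₋).

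| N | Mean positivity | n₊ | n₋ | Half-width (points) | Bias (points) |
|---|---|---|---|---|---|
| 5,000 | 2.5% (larger contrast) | 125 | 4,875 | 8.9 | 6.2 |
| 5,000 | 1.5% (milder contrast) | 75 | 4,925 | 11.4 | 1.7 |
| 300,000 | 2.5% | 7,500 | 292,500 | 1.1 | 6.2 |
| 300,000 | 1.5% | 4,500 | 295,500 | 1.5 | 1.7 |

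At 5,000 both biases lie inside the half-width. At the recruitment ceiling both lie outside it. The bias column does not depend on N.

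**The case against.** The strongest case against has four parts.

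- **Status and deferral.** Section 9.1 calls the analysis primarily descriptive and the hypothesis exploratory, and section 9 leaves details to a separate analysis plan. Section 9.2 mentions multivariable modeling. This stands as a limit: the supplied text is silent on community, and a reader should not infer that no analysis will ever account for it. It does not supply the adjustment. The contrast is still part of the primary endpoint, its test is named, and the multivariable modeling lists no covariates.
- **Size.** A reader might set 6.2 and 1.7 points against the 1.37% margin for N = 5,000 and conclude that the bias swamps the study's precision. The documents do not support that, because 1.37% belongs to a single proportion. All the rates are also assumed, so nothing here shows that the study's result will in fact be biased.
- **Feasibility.** A reader might infer from the residence criterion that community is already available for analysis. A yes/no screen would satisfy that criterion, and section 10.1.3 says the analysis data exclude contact and identifying information. Whether a community code reaches the analysis file is not stated. With an unknown number of communities and few positives, a fixed effect for each community may also be unstable in a binary mixed model.
- **Other confounders.** Symptoms are collected and could relate to both test result and distancing, yet they are equally unadjusted. This stands: community is one confounder among several.

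**Conclusion.** The point holds as a conditional weakness in the primary comparison. As written, the participant-clustered test carries any between-community confounding straight into the estimate, and none of the named stratifications removes it. With the assumed rates, the distortion is 1.7 to 6.2 points where there is no true effect, and a true 5-point difference can be reduced to about zero. This requires communities to differ in both positivity and distancing.

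At 5,000 participants with one result each, distortions of this size would sit within sampling error of roughly 9 to 11 points. They become the dominant error toward the 300,000 ceiling. The documents do not establish that the result will be biased, or that adjusting for community would make the contrast causal. The change is worth making before analysis because the specified method cannot distinguish place from response, and a better one is readily available.

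**What to change.** - In sections 9.4.1 and 9.4.2, specify the positive-versus-negative comparison as stratified by community, for example a Mantel-Haenszel risk difference with participant-clustered variance. This tolerates many or sparse strata.
- Report the crude and community-adjusted differences side by side, so that the effect of place is visible.
- Include community in the exploratory mixed models where the number of communities and of positive results allows.
- Confirm that a community code is captured and carried into the de-identified analysis file.

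**Cost.** There is slightly more analysis work and a data-handling step for the community code. Communities with no positive results contribute nothing to the stratified difference, so some information is lost. The report should also state that confounding by other factors, such as symptoms, remains after this adjustment.
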